9.3.5. Variables Collected in the Event of Discontinuation of PrEP

The reason for and the date of PrEP discontinuation will be collected. If the reason for discontinuation is related to a serious adverse drug reaction (SADR) or treatment-related renal or bone adverse reactions, this will be collected in the AE section of the eCRF. If the discontinuation is due to a withdrawal of consent, no further data will be collected. If the discontinuation is due to development of a new HIV-1 infection (ie, seroconversion), the results of any HIV diagnostic testing and genotypic resistance testing should be reported both in the registry and to the applicable country central database for HIV testing and diagnosis. Information on adherence to Truvada for PrEP along with possible factors leading to HIV-1 seroconversion should be reported.

9.3.6. Variables Collected in the Event of Loss to Follow-up

If an individual is lost to follow-up, a notation will be made on the eCRF as to the reason for the loss to follow-up, if known.

9.3.7. Site Information

Data will be collected about the sites which prescribe and/or monitor Truvada for PrEP. Data will include location (eg, country, city, urban or rural) and setting (eg, hospital, clinic, private practice). Additional data on current practice for providing Truvada for PrEP will be collected for the sites that agree to participate in the registry.

9.4. Data Sources

This observational noninterventional registry will extract data from the individual's medical record. Data obtained from clinic visits, physical examinations, and medical records, including medical history, hepatitis history, prescribed medications, laboratory results, and safety data, will be captured while participating in the registry. HCPs will enter data into eCRF at each data collection point in a timely manner. If the HCP receives queries about data entered in the eCRF from the sponsor (or designee), the HCP will review the medical record and correct the eCRF data if necessary.

9.5. Study Size

The purpose of the registry is to provide insight into the patterns of Truvada for PrEP usage and how clinicians are monitoring individuals on Truvada for PrEP. The registry is not designed or powered to compare rates of seroconversion or adherence with studies or demonstration projects.

Enrollment will be open to both adults and adolescents, and enrolled individuals will be followed while Truvada for PrEP is continued. Target is to enroll and follow enough adults to provide at least 400 person-years of follow-up data and enough adolescents to provide at least 25 person-years of follow-up data.

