Both adults (≥ 18 years of age) and adolescents weighing at least 35 kg (eg, 12 to 17 years of age) receiving Truvada for PrEP will be included as the primary population for this registry. Furthermore, the registry will collect data on HCPs who prescribe Truvada for PrEP.

Inclusion criteria:

- HIV-1 negative adults and adolescents who are deemed to be at high risk for acquiring HIV-1
- HIV-1 negative adults and adolescents who provide consent / assent and, depending on local country regulations, parental or legal guardian permission to participate in the registry
- HIV-1 negative adults and adolescents who are receiving Truvada for HIV PrEP, either as a daily or intermittent regimen, and that are clinically monitored

Exclusion criteria:

- Individuals currently participating in a clinical study of HIV PrEP

Variables: Individual data elements will be collected as available after enrollment and while participating in the registry. Data will include: age, gender at enrollment, weight and height, HIV risk factors, concurrent sexually transmitted infections, hepatitis B virus serostatus, hepatitis C virus serostatus, prior PrEP or post-exposure prophylaxis use, estimated glomerular filtration rate, serum phosphate, use of recreational drugs during sex, and PrEP adherence assessment. Pregnancy status will be requested for females. PrEP prescription/usage details will include: dose schedule, initiation (ie, prescription or self-initiation) date and stop date or duration of PrEP usage, and the tablet and refill quantity. If seroconversion occurs, additional data include date of seroconversion, circumstances of HIV acquisition if available, and results of HIV-1 resistance testing if available. Selected safety data for collection in the registry will include all fatal events, serious adverse drug reactions (SADRs), treatment-related renal or bone adverse drug reactions, and pregnancy reports. Possible factors leading to new HIV infection, genotypic resistance testing, and reason for PrEP discontinuation will also be collected.

Details on the participating institutions will include location and type of institution. HCP data will include provider specialty and if they routinely treat individuals with HIV-1 infection.

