9.3.3. Items of Surveillance

Data from routine care, as available from medical records, will be collected using electronic case report forms (eCRFs). The following elements will be collected at the approximate intervals as noted in [Table 9-1](#).

Table 9-1. Data Items and Timing for Surveillance

Items of Surveillance	On-Treatment Period		Seroconversion
	Baseline Truvada PrEP initiation	Each Follow-Up Visit	At Time of New HIV Infection
Informed consent	X		
Age	X		
Gender at start of PrEP (Male [M], Female [F], Transgender M-F or F-M)	X		
Weight and Height	X	X	
Self-initiated or prescribed Truvada for PrEP usage details (dose and schedule [continuous/daily or intermittent])	X	X	
Truvada for PrEP start and stop dates or duration of PrEP usage	X	X	X
Product name: (Truvada prescribed or self-sourced)	X	X	X
Assessment of adherence with PrEP	X	X	X
Risk factors for HIV-1	X	X	X
Use of recreational drugs during sex	X	X	X
Sexual transmitted infections – (1) oropharyngeal, (2) urethral/cervicovaginal, (3) rectal, and (4) syphilis	X	X	X
HIV-1 test method(s), results, and dates	X	X	X
Prior use of PrEP (prescribed or self-medicated) or PEP	X		
HBV serostatus	X		
HCV serostatus	X		
If female, pregnancy status	X	X	X
eGFR	X	X	
Serum phosphate	X	X	
Safety data (all fatal Events and all serious adverse drug reactions [SADRs], treatment-related renal or bone adverse drug reactions, and pregnancy reports)	X	X	X

Items of Surveillance	On-Treatment Period		Seroconversion
	Baseline Truvada PrEP initiation	Each Follow-Up Visit	At Time of New HIV Infection
Possible factors leading to new HIV infection			X
Genotypic resistance testing			X
Reason for PrEP discontinuation		X	X

Data on participating institutions and prescribers will be collected at the time of enrollment. Institution information will include country, city, and type of institution. Prescriber information will include medical specialty.

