9.9. Limitations of the Research Methods

Limitations of this registry are those common to registries, including selection bias that may limit generalizability to the general PrEP using population.

HCPs and their respective institutions must volunteer and agree to participate in the registry and thus may not be representative of all prescribers of Truvada in Europe. Uninfected individuals receiving Truvada for PrEP must also agree to participate in the registry and thus also may not be representative of all PrEP users. The ability for individuals to obtain Truvada for PrEP by the internet further complicates this issue as it is challenging to monitor or compare these individuals with those who can obtain the drug and who volunteer to participate in the registry.

As this registry may enroll HCPs and institutions less familiar with registry data collection processes or may have fewer resources available to provide data to the registry, the extent and quality of the data may be compromised. To facilitate collection of data, this registry will reduce the extent of data collected and also provide standard training at the Site Initiation Visit on how to complete the eCRF. One example is rather than collecting all AEs, this registry is proposing to collect only fatal Events, SADRs, treatment emergent renal or bone ADRs, and pregnancy reports.

Collecting data on use of Truvada for PrEP may result in data that are different from the usual manner of prescribing in accordance with the SmPC. For example, Truvada for PrEP is recommended to be taken daily. However, other dosing regimens, such as event-based dosing, may be prescribed.

Enrollment of adolescents will present additional challenges. Adolescents may be prescribed Truvada for PrEP but may choose not to participate in the registry. Participation will be further limited if parenteral informed consent is required. In the United States, prior to the broadening of the approval to include use in adolescents, drug utilization data suggested adolescents using Truvada for PrEP accounted for approximately 1.5% of Truvada for PrEP usage {[Magnuson et al 2018](#)}. Efforts will be made to enroll as many adolescents as possible; however, enrollment of a pre-established minimum recruitment number for adolescents may not be achievable.

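### Age is recorded only at PrEP start, so adolescent person-time may include time after the 18th birthday and cannot be cut exactly at 18

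*Protocol*

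**What the plan says.** Section 9.5 gives two person-time targets without a derivation. For adults: "Target is to enroll and follow enough adults to provide at least 400 person-years of follow-up data". For adolescents: "enough adolescents to provide at least 25 person-years of follow-up data". The Population paragraph of the synopsis puts adults at 18 and over and gives 12 to 17 as the example range for adolescents.

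Four other sections decide what can be known about age over time:

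- Table 9-1 (section 9.3.3) marks age in the baseline column only. Weight and height, dosing details, adherence, risk factors and eGFR are marked again at follow-up visits.
- Section 9.1 sets baseline at the start of Truvada for PrEP. It admits people who began before enrolment and takes their earlier data retrospectively.
- Section 9.3.1 defines person-time as stop date minus start date plus one day, with no reference to age.
- Section 9.6 has the eCRF built to collect the items in Table 9-1.

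Section 9.7 plans adherence and seroconversion rates with 95% confidence intervals, by subgroups that include adults and adolescents. It leaves further detail to the statistical analysis plan.

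On feasibility, section 9.9 reports that "drug utilization data suggested adolescents using Truvada for PrEP accounted for approximately 1.5% of Truvada for PrEP usage". This is a United States figure from the period "prior to the broadening of the approval to include use in adolescents". The section then warns that "enrollment of a pre-established minimum recruitment number for adolescents may not be achievable".

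**The concern.** Section 7.1 names adolescents and young adults as the groups with limited data, so the adolescent stratum is where the registry has most to add. It is also where people leave the stratum simply by ageing. Enrolment lasts 3 years and data collection runs 6 months longer. One person can therefore contribute about 3.5 years on the registry, and more if PrEP began earlier. Someone who started at 17 spends less than one of those years under 18.

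With a single age on file and no split in the person-time definition, two things follow. The 25 person-years could be reached partly with adult time. An adolescent seroconversion or adherence rate could also mix two age groups without the reader being able to tell. A later analysis rule can reduce the problem, but it cannot recover a birthday that was never collected.

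**Working it through.** **Step 1. The plan's own figure.** The 25 person-years has no stated derivation, so there is nothing to reproduce. The ENCePP checklist (item 10.6) answers no to sample size estimation.

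**Step 2. How closely the 18th birthday can be placed.** The inputs on file are age at PrEP start (Table 9-1) and PrEP start and stop dates. I assume age is held in whole years, since the protocol does not give the format. A recorded age A then means a true age from A up to A + 1, and the time from PrEP start to the 18th birthday lies between 17 - A and 18 - A years:

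- A = 17: 0 to 1 year
- A = 16: 1 to 2 years
- A = 15: 2 to 3 years

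The window is one year wide for each person. An HIV diagnosis inside it cannot be assigned to either age group with certainty. At 25 person-years, one case is 1/25 = 4 per 100 person-years, so the placing of a single case matters.

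**Step 3. Possible size, if people were classed by age at PrEP start.** This rule is an assumption; the protocol does not state it. Let true start ages be uniform from L to 18, let w = 18 - L, and let everyone be followed for F years from PrEP start.

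- If F ≤ w, a fraction F/w of people pass 18, and on average half of their follow-up comes after it. Adult share = F/(2w).
- If F > w, mean time under 18 is w/2. Adult share = 1 - w/(2F).

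| Start ages (assumed) | w | F = 1 year | F = 2 years | F = 3.5 years |
|---|---|---|---|---|
| 12-17 | 6 | 1/12 = 8% | 2/12 = 17% | 3.5/12 = 29% |
| 15-17 | 3 | 1/6 = 17% | 2/6 = 33% | 1 - 3/7 = 57% |
| 17 only | 1 | 1/2 = 50% | 1 - 1/4 = 75% | 1 - 1/7 = 86% |

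Applied to 25 nominal adolescent person-years at F = 2, the adult part is 25 × 0.167 = 4.2, 25 × 0.333 = 8.3 or 25 × 0.75 = 18.75 person-years.

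**Step 4. The target beside the one share cited (secondary).** With adults at exactly 400 person-years and a 1.5% adolescent share, adolescents give 400 × 0.015/0.985 = 6.1 person-years. The ratio is 25/6.1 = 4.1. The two targets together imply 25/425 = 5.9%. At assumed shares of 1% and 3% the result is 400 × 0.01/0.99 = 4.0 and 400 × 0.03/0.97 = 12.4 person-years.

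**The case against.** The strongest reply is that allocating person-time at a birthday is ordinary content for a statistical analysis plan, which is not at hand. That stands as far as the rule goes. Age at start plus dates gives attained age to within about a year, and a plan could work from that approximation. A reader might infer from the protocol that adult time is counted as adolescent. The documents do not support this, because nothing in them fixes a person's age group at baseline for person-time. What the reply does not reach is data capture, which this protocol fixes: sections 9.3.3 and 9.6 determine what the eCRF holds.

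It is also fair to object that the percentages depend on the start ages chosen. They do: the protocol's own example range, 12 to 17, gives the lowest row of the table. Time just after 18 also still falls within the stated data gap, which covers young adults. It is useful time, but it is not adolescent time.

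Two other strong readings fail:

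- A reader might infer that the synopsis and Table 9-1 disagree on when age is taken. The synopsis lists "age, gender at enrollment, weight and height", where the timing phrase attaches to gender. The matching row in Table 9-1, "Gender at start of PrEP (Male [M], Female [F], Transgender M-F or F-M", also concerns gender. No conflict over age is shown.
- A reader might call the 25 person-years an arithmetic error, or say that section 9.9 contradicts it. The 1.5% is a share of use in the United States before adolescent approval there, not a planning input for five European countries. Both targets are minimums with no cap on adult time, and section 9.9 promises extra effort to enrol adolescents. A target stated with an open risk of missing it is not a contradiction.

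**Conclusion.** The point holds as a defect in data capture. Age is recorded once, at a date that may precede enrolment, and person-time has no split at 18. The adolescent target and subgroup rates can therefore include time after the 18th birthday, and that time cannot be separated exactly. For each person who passes 18 the uncertainty is about one year, if age is held in whole years.

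If people were classed by age at PrEP start, the adult share at 2 years would be about 17%, 33% or 75% for start ages 12-17, 15-17 or 17 only. These figures show how large the effect could be; they do not predict what the analysis will do. They rest on the assumed rule, uniform start ages and equal follow-up.

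The size of the adolescent target is a secondary matter of wording. It is an unsupported planning figure, about four times what the only cited share would give beside 400 adult person-years.

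**What to change.** - **Table 9-1:** add age at enrolment, at each follow-up visit and at seroconversion, or collect month and year of birth where local rules allow.
- **Section 9.3.1:** split person-time at the 18th birthday.
- **Sections 9.5 and 9.7:** count only time under 18 toward the 25 adolescent person-years and the adolescent subgroup, and move later time to the adult group.

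The cost is one repeated eCRF field, best settled before the eCRF is built. The adolescent total will be smaller; the adolescent rates could move in either direction. Month and year of birth places the birthday to within a month. Age in whole years at visits places it only between two visits, so its precision depends on how often people attend.

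Optionally, section 9.5 could cross-refer to section 9.9 and note that the cited share of about 1.5% (United States, before adolescent approval) would give about 6 adolescent person-years beside 400 adult ones. This needs only a sentence.

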9.6. Data Management

After finalization and approval of the protocol, an eCRF will be built in a commercial electronic data capture (EDC) system to collect the data listed in the variables section ([Table 9-1](#)). Personal identifying data such as names, health record identifiers, and national insurance numbers will not be collected.

HCP participants from each site will receive a unique username and password from the EDC system administrator following completion of the EDC system training. Completion of training and receipt of username/password will allow sites to enter data into the eCRF. HCPs will electronically sign the eCRF to confirm responsibility for the data following completion of data entry and data quality activities. Registry data will be stored on secure network drives with access restricted to authorized personnel only.

9.7. Data Analysis

Descriptive data analysis will be used to summarize the available data. There are no statistical hypotheses to evaluate. Categorical variables will be reported by proportions and continuous variables will be reported by mean, standard deviation, minimum, median, and maximum. Prescriber characteristics will be summarized. Demographics and clinical characteristics of individuals on Truvada for PrEP will be analyzed. The products prescribed and available prescription details, the frequency of monitoring, and any relevant data on adherence monitoring will be summarized. Seroconversion cases and results of resistance testing will be summarized. Reports of treatment-related renal and bone adverse drug reactions (SADRs and ADRs) will be summarized. Females participants in the registry who are pregnant will also be analyzed.

Data will be presented overall, and by age group (adolescents and young adults) and risk factors for HIV transmission.

Rates of adherence and new HIV diagnoses (i.e., seroconversion) will be calculated with 95% confidence intervals. Results will be presented overall and by subgroups including adults and adolescents, gender, and country.

Comprehensive information relating to the analysis of this registry will be provided in the statistical analysis plan.

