8. RESEARCH QUESTIONS AND OBJECTIVES

The objectives of this registry are as follows:

- To describe how Truvada for PrEP is prescribed or self-initiated, including the dosing pattern (dose and schedule as daily/intermittent)
- To characterize the demographics of adults and adolescents who are receiving Truvada for PrEP and their HIV risk factors
- To characterize the nature and frequency of individual monitoring after initiating Truvada for PrEP, including any available information on adherence
- To document any cases of new HIV diagnoses and development of any resistance to Truvada and selected safety data
- To summarize the characteristics of healthcare professionals who prescribe Truvada for PrEP

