9. RESEARCH METHODS

9.1. Study Design

This is a prospective, longitudinal, observational, and voluntary participation registry designed to characterize the real-world use of Truvada for PrEP to prevent HIV-1 infections in adults and adolescents in Europe. The individuals who agree to participate in the registry will receive treatment solely based on current clinical practice in the country in which they reside. The use of Truvada for PrEP should be within the conditions of its approved SmPC. However, Gilead will not influence decision making by the participating HCPs or restrict enrollment into the registry to those individuals who are not receiving drug in full compliance with the SmPC (where local regulations allow to do so) as the objective of the registry is to describe the patterns of use and monitoring in real life. Data on intermittent use of Truvada for PrEP will be collected in countries permitting such data collection.

Both male and female adults and adolescents will be recruited for enrollment in the registry. Individuals who started Truvada for PrEP prior to first presenting to the participating HCP or are prescribed Truvada for PrEP will be eligible for enrollment. Baseline will be considered as the start date of Truvada for PrEP. The data for individuals receiving Truvada for PrEP prior to enrollment will be collected retrospectively from the individual's medical record.

Individuals will be followed while on Truvada for PrEP and the frequency of clinic visits will be at the discretion of the prescribers. Individuals will be followed until they are either lost to follow up, discontinued Truvada for PrEP, become infected with HIV, withdraw consent, or registry closure.

Details on Truvada for PrEP use, the healthcare Institution characteristics, and prescriber characteristics will also be collected .

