Recruitment methods within each country will begin by assessing if they have a national policy for PrEP or a similar initiative that would support reimbursement of all HIV-1 PrEP medicinal products or only Truvada or generic equivalents products. HCPs who prescribe products for HIV-1 PrEP will be contacted to determine if they prescribe Truvada for PrEP and if so they will be invited to participate in the registry. Additionally, a review of planned, ongoing, or completed clinical studies or demonstration projects which include Truvada for PrEP will be carried out to identify potential individuals who have completed or discontinued participation in the study but continue to take Truvada for PrEP.

A written contract on the implementation of this registry shall be concluded between sponsor and clinical site. Personnel from the sponsor company or the contract research organization (CRO) will describe the registry to HCPs at each site and provide training on the registry design and data collection to ensure, as much as possible, quality and consistency of data collected. HCPs will only be compensated for their time and efforts on the registry based on current fair market value at the time of contract finalization.

9.2.1. Inclusion Criteria:

- HIV-1 negative adults and adolescents who are deemed to be at high risk for acquiring HIV-1
- HIV-1 negative adults and adolescents who provided consent / assent and, depending on local country regulations, parental or legal guardian permission to participate in the registry
- HIV-1 negative adults and adolescents who are receiving Truvada for HIV PrEP, either as a daily or intermittent regimen, and that are clinically monitored

9.2.2. Exclusion Criteria:

- Individuals currently participating in a clinical study of HIV PrEP

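### New and prior Truvada users are pooled on a clock that starts at PrEP initiation, so rates include time in which prior users could not have an event counted

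*Protocol*

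**What the plan says.** Protocol Section 9.1 sets who may enter: "Individuals who started Truvada for PrEP prior to first presenting to the participating HCP or are prescribed Truvada for PrEP will be eligible for enrollment". It also fixes the time origin, "Baseline will be considered as the start date of Truvada for PrEP", and the source of earlier data: "The data for individuals receiving Truvada for PrEP prior to enrollment will be collected retrospectively from the individual's medical record". The inclusion criteria in Section 9.2.1 cover "HIV-1 negative adults and adolescents who are receiving Truvada for HIV PrEP, either as a daily or intermittent regimen, and that are clinically monitored".

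Section 9.3.1 counts person-time from the PrEP initiation date to the end date. It is the only person-time definition in the protocol. Section 11.1.1 starts safety collection at consent, and Section 11.3.1 classes conditions with onset before consent as pre-existing rather than as adverse events.

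Section 9.7 plans rates of adherence and of new HIV diagnoses with 95% confidence intervals. On presentation it says "Results will be presented overall and by subgroups including adults and adolescents, gender, and country"; a separate sentence adds age group and HIV risk factors. New versus prior user appears in neither list. Section 9.9 discusses the fact that prescribers and users volunteer, but not selection through having already stayed on the drug. In the ENCePP checklist (Annex 1), exposure time windows (item 5.3) and selection and time-related bias (7.2.1, 7.2.2) are marked not applicable; item 12.1.1 points to Section 9.9 for selection bias.

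**The concern.** A person who started before enrollment can enter only if still on Truvada, still HIV-1 negative and still attending a clinic. Those who stopped early, seroconverted early or left because of an early reaction are not there to be enrolled. A new starter is observed through that same early period with every outcome possible. The protocol puts both on one clock running from initiation.

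Two things follow. First, the planned results on adherence and on monitoring after initiation mix a full view of the early period with a view that excludes those who left during it. Second, for seroconversion the pre-enrollment time of prior users can enter the denominator although no event could have occurred in it. The same holds for any reaction frequency per unit of exposure, because reactions before consent are not collected as safety events.

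Section 9.7 also presents results by country. If countries differ in their mix of prior and new users, part of any difference between them may come from that mix alone.

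**Working it through.** There is no plan figure to reproduce. Section 9.5 gives person-time targets without a rate, precision or power calculation.

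**Are prior users likely to be few?** Section 9.1 sets no cap or quota. Section 9.2 has prescribers assess all users at routine visits, and it searches for former study and demonstration-project participants who continue on Truvada. Section 7.1 dates the PrEP indication to August 2016, and Section 6 targets the start of data collection for the end of Q4 2020, about four years later. Prior users will be present; their share is not stated.

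**Inputs.** Targets of 400 adult and 25 adolescent person-years (Section 9.5). Rates of 0.4 per 100 person-years in an adult demonstration project and 6.4 in a single-arm adolescent trial (Section 7.1), used only as reference values. The share f of person-time that precedes enrollment is assumed, at 0 to 75%.

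**At target, f = 0.** Expected seroconversions are 400 × 0.004 = 1.6 in adults and 25 × 0.064 = 1.6 in adolescents. The chance of seeing none is e^(−1.6) = 0.20 in each group.

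**Effect of f.** With a constant rate, events can occur only in the share (1 − f), while the denominator holds all the time:

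reported rate = rate × (1 − f)

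| Assumed f | Adults, per 100 PY | Adolescents, per 100 PY | Expected events at target (each group) |
|---|---|---|---|
| 0 | 0.40 | 6.4 | 1.6 |
| 25% | 0.30 | 4.8 | 1.2 |
| 50% | 0.20 | 3.2 | 0.8 |
| 75% | 0.10 | 1.6 | 0.4 |

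The last column assumes that the person-year targets are counted as exposure under Section 9.3.1. If they cover only time after enrollment, the expected events stay at 1.6, but a rate over initiation-based exposure still shrinks by (1 − f).

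**Effect on the interval.** With no events, the exact 95% upper limit is −ln(0.025) = 3.69 divided by the person-years. That gives 3.69/400 = 0.92 per 100 person-years in adults and 3.69/25 = 14.8 in adolescents. If half of that time preceded enrollment, the time truly at risk would be 200 and 12.5 person-years, and the limits should be 1.84 and 29.5. The reported upper limit would be half of what the data support.

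**Countries.** Two countries with the same adult rate of 0.4, one with f = 25% and one with f = 75%, would be expected to report 0.30 and 0.10.

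**Adherence and monitoring.** The documents give no basis for a number. The adherence result is pulled toward people who persisted, and the period just after initiation, which the monitoring objective in Section 8 addresses, is where the selection acts.

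**The case against.** The strongest reply is that the registry aims to describe everyone currently taking Truvada for PrEP, and that Section 9.5 disclaims any comparison of seroconversion or adherence rates with other studies. For that purpose a pooled figure is a legitimate description. This stands, and it is why the overall figure should remain. It does not justify counting, in a seroconversion rate, time in which entry rules exclude the event.

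A second reply is that the subgroup list in Section 9.7 is open and that detail is left to the analysis plan. This stands for table layout: absence from an open list is not a decision against the split. The time origin, entry condition and start of safety collection, however, are fixed in the protocol itself.

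A third reply is that earlier data are gathered retrospectively, and that Table 9-1 marks safety data at baseline. Retrospective records cannot restore people who were never eligible, and Sections 11.1.1 and 11.3.1 set consent as the start.

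A reader might infer more than the documents support:

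- **Prior users dominate the results.** No share is given, so this cannot be said.
- **Discontinuation or reaction rates will be understated.** Section 9.7 announces neither. Reasons and dates of stopping are collected (9.3.5), and reaction reports are to be summarized.
- **Objective 1 is left unanswered because prescribed and self-initiated use are not contrasted.** The objective, "To describe how Truvada for PrEP is prescribed or self-initiated", is descriptive. Table 9-1 collects the route of initiation, and the synopsis counts it among prescription and usage details. A stratum by route is optional, not a missing analysis.
- **New users must become the main analysis set.** That would change the registry's target population.

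**Conclusion.** The point holds in a limited form. The protocol combines entry conditional on being on drug and HIV-1 negative, a clock that starts at initiation, and safety collection that starts at consent, and it names no new-versus-prior-user split. Adherence, post-initiation monitoring and seroconversion results, and any reaction frequency per exposure, are shifted toward people who stayed on drug. For seroconversion the factor is (1 − f), assuming a constant rate and exposure as defined in Section 9.3.1 as the denominator; f is unknown. With about 1.6 events expected per age group at best, sampling error will be large in any case, but the dilution acts in one direction and also narrows the interval. This is an inexpensive improvement to reporting; it does not invalidate the registry.

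**What to change.** In Section 9.7, keep the overall figure and label it as a description of current users. Beside it, report adherence, monitoring after initiation, seroconversion and adverse drug reactions for two groups:

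- **New users:** first Truvada start at or after enrollment.
- **Prior users:** any Truvada start before enrollment, including those who stop and restart later. This settles where the repeat exposures allowed by Section 9.3.1 belong.

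For prior users, count at-risk time for seroconversion and safety from enrollment (delayed entry), and say so in Section 9.3.1 or 9.7. Delayed entry removes the mismatch between events and time; it does not undo the selection of who remained, so the separate columns are needed as well. Add to Section 9.9 that prior users are selected by having stayed on drug. Prescribed versus self-initiated use may be added as a descriptive split.

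Start dates, prior PrEP use and consent are already in Table 9-1, so no new data items are needed. The cost is extra columns and smaller cells. This weighs most in adolescents, where the target is 25 person-years and Section 9.9 already doubts that a minimum number can be recruited; there, counts with person-time may be all that can usefully be shown.
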